iPhone® Helping Evaluate Atrial fibrillation Rhythm through Technology (iHEART) Study (NCT02731326)

IRB approval: August 15, 2020

Study Design

The iPhone® Helping Evaluate Atrial fibrillation Rhythm through Technology (iHEART) study is a single-center, prospective, randomized controlled trial (RCT) (**Figure 1**). The primary aims of the iHEART study are to: (1) Examine the efficacy of mHealth ECG technology (iHEART intervention) on the detection and treatment of recurrent AF as compared to usual cardiac care (control group); (2) Evaluate the quality-adjusted life-years (QALYs) in those in the iHEART intervention as compared to the control group between baseline and 6 months; (3) Determine the impact of behavior altering, motivational text messages on chronic cardiovascular conditions (e.g., hypertension, diabetes) and AF knowledge over 6 months. Participants are randomized to one of two groups: iHEART (intervention group) or usual care (control group). All participants enrolled will be followed for a period of 6 months. This study protocol adheres to the appropriate standards of reporting as stated in the Standard Protocol Items: Recommendations for Interventional Trials statement and facilitates the methodology of the Consolidated Standards of Reporting Trials statement for later dissemination of the results of the outlined RCT.

Study Population

Patients will be screened for eligibility (**Table 1**). Those who meet inclusion criteria will be approached for enrollment after the patient's provider agrees to the study protocol and is willing to receive and review ECG transmissions. The details of the study will be explained in English or Spanish, and patients will be given an opportunity to ask questions before signing informed consent. A copy of the consent form will be given to the patient.

Inclusion criteria will include documented AF that has been treated in the last 30 days resulting in the restoration of normal sinus rhythm. The operational definition of AF for this study will include the presence of AF captured by the AliveCor® Mobile ECG, a standard 12 lead ECG, Holter, or any other external recording mechanism that documents AF. Over a six-month period, those individuals with \leq 7 days of AF will be considered paroxysmal, and those with greater than 7 days of continuous AF will be defined as persistent AF per the AHA/ACC/HRS guidelines. The main exclusion criteria for participants include documented permanent (chronic) AF, unwillingness to use technology and have one's clinical data collected over the study period, unwillingness to receive and read cardiovascular text messaging three times a week, and patients who have a documented medical history of cognitive impairment.

Data and Safety Monitoring

The study was approved by the Columbia University Medical Center Institutional Review Board. Participants provide written informed consent prior to enrollment and all data collection procedures are in accordance with the Health Information Portability and Accountability Act regulations.

Sample Size

A total of 300 participants with documented AF who are undergoing clinical treatment of their AF with electrical cardioversion, radiofrequency ablation and/or medical management to restore normal sinus rhythm will be enrolled. After a normal rhythm is restored, participants will be randomized to usual cardiac care (n= 150) or usual cardiac care plus the iHEART intervention (n= 150). The population will be recruited from the Columbia University Medical Center (CUMC) cardiac services and will include English and Spanish speaking participants.

Randomization

The randomization process will be performed by a random computer number generator in a one-to-one block allocation ratio. In order to achieve a balance of applicable participant characteristics in both the intervention and control groups, participants will be stratified based on age and gender.

Outcome assessments

Upon study entry, all relevant clinical data will be collected at baseline and monthly throughout six months via an electronic medical records system review. This will be used to capture and quantify cardiac outcomes in both groups. In addition, all outside medical records will be requested, and participants will be contacted monthly to capture any hospitalizations, cardiac events, or changes in therapy that may occur outside of our center and clinics. AF in the usual care group may be detected during routine follow-ups with providers, as well as during self-evaluations such as a pulse check initiated as a result of participant-reported symptoms or changes in health status. AF may also be captured by a 12-lead ECG, pulse check, or heart sound auscultation during an exam that reveals an irregular heart rhythm. Participants in the usual care group may seek medical evaluation by their providers because of a change in their health status or symptoms (shortness of breath, palpitations, fatigue), which may lead to further cardiac monitoring or testing (e.g., echocardiogram) that may reveal AF. This could include Holter monitoring (24 hour) or extended cardiac monitoring (7-30 days) that may document AF and be the basis for changes in treatments prescribed by their providers (e.g., medication changes or dosage adjustments, cardioversion). In the intervention group, AliveCor® Mobile ECG transmissions will be read daily to detect recurrence of AF or other arrhythmias. All results and any treatment changes due to mobile ECG findings will be recorded over the course of the study period.

All study participants will be asked to complete a series of questionnaires including the Atrial Fibrillation Knowledge Scale (AFKS), the Canadian Cardiovascular Society Severity in Atrial Fibrillation scale (CCS-SAF), the Atrial Fibrillation Effect on Quality of Life (AFEQT), the Control Attitudes Scale-Revised (CAS-R), the Morisky 4-item Self-Report Measure of Medication-Taking Behavior (MMAS-4), the Self-Efficacy for Appropriate Medication Use Scale (SEAMS), the Short Form Health Survey (SF-36 Quality of Life), European Questionnaire 5 Dimensions (EQ-5D), the Patient Health Questionnaire (PHQ-9), and the State Trait Anxiety Inventory (STAI). These measures will be administered to both the intervention and control groups at baseline prior to any procedures, such as a cardioversion or ablation, and again at the 6-month follow-up visit for the purpose of comparison.

Study Intervention

Participants randomized to the iHEART intervention will receive an iPhone® and cellular service plan with unlimited data/text messaging, the AliveCor® Mobile ECG, and Behavioral Altering Motivational (BAM) text messaging three times a week for six months. BAM is an in-house database that automatically sends one-way text messages to the intervention participant related to their AF, as well as two underlying cardiovascular risk factors of their choosing.

AliveCor™ Heart Monitor

The AliveCor® Mobile ECG, an FDA-approved smartphone technology, works through a free application, "Kardia." It captures a highly sensitive (98%), specific (97%), and accurate (97%) single-lead ECG recording through two electrodes on the back of the smartphone[7]. When the application is opened, recording begins automatically when both electrodes make contact with skin (Figure 2). Transmissions are automatically uploaded to the study portal within the

AliveCor® “cloud”. All participants will receive in-person training on the use of the study equipment at enrollment. A return demonstration from the participant to the research coordinator will be required at baseline enrollment. This will include how to capture an ECG daily and in the setting of symptoms, as well as how to record any associated symptoms in the application.

All ECG images and any associated symptoms will be sent via WiFi or cellular network transmission to the AliveCor® cloud. A login will occur daily to the password-protected study database that will be stored on the AliveCor® cloud in order to review and interpret all ECG strips transmitted during the previous 24 hours. Any clinically significant arrhythmias, including AF or other arrhythmias, detected during the daily review of ECGs over the 6-month period will be immediately sent to the provider caring for the participant. The study team will ensure the provider has received the transmission, is aware of any ECG abnormalities, and will then be responsible for communicating such findings.

Smartphone

The study is innovative in its use of mHealth and widely available smartphone technology, which allows rapid two-way communication between patients and healthcare providers, rather than waiting for office or clinic visits that delay care. An FDA-approved smartphone technology is being used, the AliveCor® Mobile ECG to capture and send ECG data via WiFi or cellular network for immediate interpretation. Transmission of a normal ECG while a patient is experiencing a symptom with multiple underlying diagnoses impacts immediate triage and treatment of the symptom. The AliveCor® technology allows clinicians to correlate symptoms with heart rhythms.

Unlike previous ECG technology, the AliveCor® Mobile ECG is not worn, so it eliminates the need for adhesive ECG electrodes and skin patches placed on the chest and does not require complicated changing of leads by the subject. This is a significant improvement from previously available technology. The use of tailored cardiac behavior altering motivational (BAM) text messaging sent to an individual's smartphone to improve AF awareness and knowledge, as well as self-management of pre-existing chronic cardiovascular conditions associated with AF will be simultaneously evaluated.

Behavior Altering Motivational (BAM) Text Messaging

BAM one-way text messages are sent to the intervention participant three times per week and pertain to their AF, as well as two underlying cardiovascular risk factors of the patient's choosing (weight management, physical activity, hypertension, heart failure, diabetes, etc.). Starting on the day of enrollment, intervention participants will receive text messages every Wednesday related to AF management, as well as a message on Monday related to risk factor one and a message on Friday related to risk factor two. BAM text messages will be systematically selected from a bank of text messages developed through collaboration by the study team and an expert interdisciplinary panel from the American Heart Association. All messages are available in English and Spanish according to participant preference.

Control Group (Usual Care)

Participants randomized to usual care will continue their guideline-directed clinical management and follow-up as determined by their providers' interpretation of the 2014 ACC/AHA/HRS Guideline for the Management of Patients with Atrial Fibrillation.

Study end-points

The primary endpoint is detection of recurrence of AF. Secondary endpoints include treatment changes as a result of early detection of AF recurrence, study questionnaire scores at baseline and six months, including QoL, QALYs, and improvement in cardiovascular measures (e.g., blood pressure, glucose levels) and AF knowledge from baseline to 6 months. Outcome assessors will be blinded to group allocation.

Statistical Analysis

We will define and calculate recurrent AF detection rate as the ratio of the number of recurrent AF episodes to the number of person-months of follow-ups. We will compare the difference in recurrent AF detection rate over the six-month study period between the control group and the iHEART intervention group. Analysis of the potential moderating effects of demographic factors (e.g., age, gender, etc.) as well as the difference between the groups will be performed using multivariate Poisson regression.

We will compare the time-to-treatment between the iHEART intervention group and the control group with the application of survival analysis methods. For those who are treated for recurrent AF, the time-to-treatment is the time from beginning of study to the time of treatment. Those who are not treated for recurrent AF will be censored at the end of the sixth month, or the time of death should a subject die before the sixth month. We will apply the Cox proportional hazard model to examine and test the difference in the time-to-treatment between the intervention group and control group, with the adjustment for other potential confounders (e.g., age, gender). QALYs are calculated as follows: for each month of life lived at an EQ-5D index of x , the QALYs will be $x/12=0.0833x$ years. We will calculate QALYs during the 6-month study period for all participants by summarizing QALYs from baseline through sixth month. We will compare QALYs between the iHEART intervention group and the control group using a two-tailed independent sample t-test. To adjust for potential confounders (e.g., age, gender), multivariate linear regression models will be used. Additionally, we will compare change of quality of life (QoL) and symptoms of AF scores (AFEQT, AFKS, EQ5D and CCS-SAF scales, etc.) from baseline to 6 months between the two groups and between those with and without AF using linear mixed models (growth model).

Figure 1. Flowchart for Study Procedures

[figure not shown]

Table 1. Inclusion and Exclusion Criteria

Inclusion Criteria

- Males and females (English or Spanish speaking) age ≥ 18 years with a prior history of AF in the last 30 days that was treated and normal rhythm restored
- Already utilizes a smartphone prior to enrollment
- Ability to successfully use the AliveCor™ Heart Monitor, capture a baseline ECG, and transmit on the day of enrollment
- Demonstrated ability to receive and read text messages on the day of enrollment
- Willingness to complete the study questionnaires at baseline and 6 months

Exclusion Criteria

- Documented permanent (chronic) AF
- Unwillingness to have their clinical data collected over the study period
- Unwillingness to receive and read cardiovascular text messaging three times a week.

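### Aim 3 asks what the text messages do, but the design can estimate only the effect of the whole iHEART package against usual care

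*Combined protocol and SAP*

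**What the plan says.** Study Design names three primary aims:

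- Aim 1 is to "Examine the efficacy of mHealth ECG technology (iHEART intervention) on the detection and treatment of recurrent AF", compared with usual cardiac care.
- Aim 2 compares QALYs "in those in the iHEART intervention as compared to the control group between baseline and 6 months".
- Aim 3 is to "Determine the impact of behavior altering, motivational text messages on chronic cardiovascular conditions (e.g., hypertension, diabetes) and AF knowledge over 6 months". It names one component of the intervention and no comparator.

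Study Design and Sample Size describe two randomised groups of 150: usual care, and usual care with the iHEART intervention added. Study Intervention gives every intervention participant an iPhone and "cellular service plan with unlimited data/text messaging", the mobile ECG, "and Behavioral Altering Motivational (BAM) text messaging three times a week for six months". The messages concern AF "as well as two underlying cardiovascular risk factors of their choosing". The AliveCor section adds daily reading of the transmitted strips, with significant arrhythmias passed to the treating provider. No texts or study device are described for the control group.

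The Smartphone section says that the use of the texts to improve AF knowledge and self-management will be evaluated at the same time as the ECG technology. Study end-points lists cardiovascular measures (blood pressure and glucose are the examples) and AF knowledge as secondary endpoints. Statistical Analysis compares scale scores between the two groups and between those with and without AF. It has no comparison specific to the texts.

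**The concern.** Aim 3 and the Smartphone sentence promise a finding about the texts. The participants who receive texts are exactly those who receive the phone, the ECG device, the daily reading and the provider notification. A difference between arms in AF knowledge or blood pressure could come from any of these or from several together.

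The other components cannot be set aside as inert on the strength of the documents. Participants record ECGs daily and when they have symptoms, and log the symptoms. The Smartphone section presents the technology as a route to rapid communication with clinicians, and treatment changes prompted by the ECG are to be recorded. Each of these could plausibly affect AF knowledge or risk-factor control.

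The result could be reported as evidence for a texting programme when texts were never tested without the rest. The aims also disagree with each other. Read literally, the same contrast between arms is credited to the ECG technology in Aim 1, to the intervention as a whole in Aim 2, and to the texts in Aim 3.

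**Working it through.** The plan gives no figure to reproduce on this point beyond the arm sizes: 150 + 150 = 300, which agrees with Sample Size. The question is whether the text effect is identified.

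**Inputs.** Two randomised groups (Study Design); 150 per group (Sample Size); contents of the intervention arm (Study Intervention, AliveCor section); contents of the control arm (Control Group).

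**Step 1: arm means.** Let the mean outcome be a + P·phone + E·ECG + T·text, with the daily reading and provider notification counted under ECG.

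| Arm | Intercept | Phone and plan | ECG | Texts |
|---|---|---|---|---|
| Usual care | 1 | 0 | 0 | 0 |
| iHEART | 1 | 1 | 1 | 1 |

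The matrix has 4 columns and rank 2. A contrast can be estimated only if it lies in the row space.

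- Package: iHEART row minus usual-care row = (0, 1, 1, 1), so P + E + T is estimable.
- Texts alone: (0, 0, 0, 1) is not a combination of the two rows, so T is not estimable.

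Put differently, suppose the true difference between arms is D. Then (P, E, T) = (0, 0, D) and (0, D, 0) give identical arm means, and no data from this trial can tell them apart.

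**Step 2: sample size.** More participants only repeat the same two rows. At 150 or 1,500 per arm the rank is still 2.

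**Step 3: change from baseline.** With two time points, a common baseline mean, a time effect and three component-by-time effects, there are 5 parameters and rank 3. T is not estimable.

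**Step 4: the planned contrast by AF status.** Adding AF status and AF-by-time gives 7 parameters and rank 5. T is still not estimable, and P + E + T still is. AF status does not help because, within each AF group, the two arms differ by the same three components.

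**Step 5: fewer components.** If phone and ECG are merged into one component, the two-arm matrix still does not identify T. It would with a third arm receiving everything except the texts.

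**Step 6: variation inside the intervention arm.** The texting section gives every intervention participant three messages a week, with the AF message on Wednesdays, so frequency does not vary. Participants pick their own two risk-factor topics, so comparing outcomes for chosen and unchosen topics would not be a randomised comparison. Statistical Analysis does not plan one.

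**The case against.** The strongest reply is that this is wording and that the operative sections are already sound. Study Intervention defines the package openly, the endpoint definitions do not credit the texts, the planned score analysis compares the two groups, and no planned analysis claims to isolate a text effect. The affected endpoints are secondary, and AF detection, the primary endpoint, is untouched. The Smartphone sentence sits in a rationale paragraph and does not mention blood pressure or glucose. Splitting the package into three components is an analyst's choice, and because Table 1 requires everyone to use a smartphone already, the supplied phone may add little. Aim 1 already identifies its technology with the iHEART intervention, so editing it is optional.

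Much of this stands. The planned comparison between arms is valid, no harm to the data has been shown, the realistic rival explanation is the ECG with its reading and notification rather than the phone, and the Aim 1 edit is only for consistency. That Statistical Analysis names no model for blood pressure or glucose is a separate gap, which rewording Aim 3 does not close.

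None of it makes the text effect estimable: Step 5 gives the same answer with fewer components. Nor is Aim 3 obviously shorthand, since Aim 2 uses package wording in the same sentence. Because the rest of the plan already follows the package contrast, the aim is the part to change.

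**Conclusion.** The concern holds. Aim 3, as worded, asks for an effect that this design cannot estimate at any sample size; the trial can estimate the effect of the iHEART package against usual care. This conclusion rests only on the arm contents and the two-group allocation, and no effect sizes are assumed.

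Reading the difference between arms as a text effect would require assuming that the phone, the ECG and the provider contact together contribute nothing to AF knowledge, blood pressure or glucose. The documents neither state nor justify that assumption. They also give no information on the effects of the other components, so the size of any misattribution is unknown and could be zero. The consequence is confined to what may be concluded on these secondary endpoints. It matters because Aim 3 is listed as a primary aim.

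**What to change.** Make these wording changes:

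1. **Study Design, Aim 3.** Restate as: determine the effect of the iHEART intervention (iPhone and service plan, mobile ECG with daily review and provider notification, and text messages), compared with usual care, on cardiovascular measures and AF knowledge over 6 months.
2. **Smartphone.** Align the sentence on evaluating the texts, so that they are evaluated as part of the package.
3. **Statistical Analysis.** Add a sentence stating that conclusions on AF knowledge and cardiovascular measures, including blood pressure and glucose, apply to the package and not to the texts alone.
4. **Study Design, Aim 1 (optional).** Describe the intervention as the same package, for consistency.

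The cost is a narrower claim, with no statement about texts alone. No patients, visits or arms are added.

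If the sponsor needs a text-specific answer, wording is not enough: an arm or factor separating the texts would be required. As an illustration, assume two-sided alpha 0.05 and 80% power (neither is in the documents). The detectable difference in SD units is (1.96 + 0.84) × √(2/n). At 150 per arm this is 0.32. With 300 split into three arms of 100 it is 0.40 for each pairwise contrast, and power for 0.32 falls to 63%.

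### For patients treated by cardioversion or ablation, the baseline questionnaires are timed before a procedure that eligibility requires to be already done, so baseline and the time origin have no common anchor

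*Combined protocol and SAP*

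**What the plan says.** The plan describes the order of events in several places.

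- **Study Population.** Entry requires "documented AF that has been treated in the last 30 days resulting in the restoration of normal sinus rhythm". On order, "Those who meet inclusion criteria will be approached for enrollment".
- **Table 1.** The same criterion, again in the past tense: "prior history of AF in the last 30 days that was treated and normal rhythm restored".
- **Sample Size.** "A total of 300 participants with documented AF who are undergoing clinical treatment of their AF" are to be enrolled, by electrical or catheter procedure or by drugs. Then: "After a normal rhythm is restored, participants will be randomized", 150 to each arm.
- **Outcome assessments.** "These measures will be administered to both the intervention and control groups at baseline", and the same sentence fixes the time as "at baseline prior to any procedures, such as a cardioversion or ablation". The battery has ten instruments, including the EQ-5D, and is repeated only at 6 months.
- **Behavior Altering Motivational (BAM) Text Messaging.** Intervention participants start receiving messages on the day they enrol.
- **Statistical Analysis.** QALYs are accumulated from baseline to month 6. Time-to-treatment runs from the start of the study. The primary rate is divided by person-months of follow-up. None of these origins is tied to consent, procedure, rhythm restoration or randomisation.

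**The concern.** Two sequences are in play. In one, the patient is treated, rhythm is restored, and enrolment follows. In the other, the patient enrols and answers the questionnaires, is then treated, and is randomised once rhythm is restored. A coordinator cannot follow both for a patient treated by procedure, and different coordinators may resolve the conflict differently.

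Three things are at stake:

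- **Meaning of the scores.** A score taken before the procedure describes a patient not yet restored to sinus rhythm. The change to 6 months then includes the effect of the index procedure. QALYs, which are part of a primary aim, start from a state that ended before the randomised comparison began.
- **Consistency across patients.** If some baselines precede the procedure and others follow it, the scores measure different states.
- **The clock.** If it starts before restoration, the index treatment could be counted as a treatment event, and follow-up would include time in which a recurrence cannot yet occur.

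**Working it through.** **1. The plan's own count.** 150 + 150 = 300, which matches the stated total exactly. The documents give no power, effect size or AF rate, so nothing further can be reproduced.

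**2. Three types of patient tested against the text.**

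- *Cardioverted or ablated within the last 30 days, in sinus rhythm.* Meets Table 1 and Study Population. Cannot complete the battery before the index procedure.
- *Enrolled ahead of a planned cardioversion or ablation.* Fits the questionnaire timing and the Sample Size text. Does not yet meet Table 1. Has no arm on the day of enrolment, because randomisation waits for restoration, yet the BAM section needs the arm to be known that day.
- *Restored by drugs alone.* Has had no procedure, so can meet both Table 1 and the questionnaire timing.

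The conflict between eligibility and baseline timing is thus confined to patients treated by procedure. The documents do not say what share of the 300 they are.

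**3. Effect on each analysis.**

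- *Between-arm comparison of QALYs and change scores.* If the baseline is taken before allocation is revealed and timed alike in both arms, the shift is the same in expectation on both sides and cancels. Mixed timing adds variance.
- *Absolute QALYs and within-group change.* These do not cancel. They include the index procedure's effect or not, depending on timing.
- *Patients with against without AF.* This comparison is not randomised. Timing depends on how the patient was treated, which may be related to recurrence, so mixed timing can distort it.
- *Cox model and person-months.* With no defined origin, the period before restoration may be inside or outside the clock.

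**4. Illustrative size for QALYs.** The plan credits x/12 years for each month at EQ-5D index x, but EQ-5D is measured only at baseline (x0) and month 6 (x6), and no rule is given for the months between.

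Assume a straight line:

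QALY = 0.5 × (x0 + x6)/2 = 0.25·x0 + 0.25·x6

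The baseline score therefore carries a weight of 0.25 years, and a gap d between the pre-procedure and post-restoration index shifts the QALYs by 0.25 × d. The gap is my assumption; the documents give none.

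- d = 0.05: 0.25 × 0.05 = 0.0125
- d = 0.10: 0.25 × 0.10 = 0.025
- d = 0.15: 0.25 × 0.15 = 0.0375

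The 6-month maximum is 6 × 1/12 = 0.5, so these are 2.5%, 5% and 7.5% of it. If the baseline value were instead carried forward, the weight would be 0.5 and the shifts would double, to 0.025, 0.05 and 0.075.

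**The case against.** The best defence is that this is loose wording around a single enrolment day. Training takes place at enrolment, the qualifying ECG is transmitted that day, and the messages start then. Baseline and randomisation could easily share that date. The procedures mentioned in the questionnaire sentence might be later ones during follow-up, since the same section lists cardioversion among possible treatment changes. Figure 1, the flowchart, could not be read in the text available to me and may show the order.

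The single-day reading is plausible, but under it the questionnaire timing still cannot be met for patients already treated by procedure. The later-procedures reading is weaker: nothing in the sentence says so, Sample Size names the same procedures as the index treatment, and its enrolment of patients still under treatment would remain unexplained. If Figure 1 gives the order, the text still has to agree with it.

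Two parts of the defence stand in full. Uniform timing does not bias the randomised contrast, and the primary endpoint uses no questionnaire score, so it is touched only through the origin of person-months.

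A reader might also infer that the total of 300 is contradictory. It is not: the arm sizes are stated for those randomised and add up. A shortfall would need enrolment before restoration, some patients never restored, and no replacement, and the documents establish none of these.

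**Conclusion.** The conflict is real for patients restored by cardioversion or ablation and should be resolved, because for them the plan cannot be carried out as written. The consequence is moderate. It concerns the meaning of absolute QALYs and change scores, the precision of baseline-based analyses if timing is mixed, the non-randomised comparison by AF status, and the origin of the clock. The QALY shift of 0.0125 to 0.0375 per affected patient rests on an assumed EQ-5D gap of 0.05 to 0.15 and on straight-line interpolation, neither of which comes from the plan. It is not an estimate of bias between arms.

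Two stronger readings should be resisted. A reader might call time zero contradictory. It is one undefined term, made ambiguous by the baseline conflict. A reader might also take the 30-day eligibility window as the longest gap between baseline and randomisation and compute a share of follow-up from it. That window looks back to earlier treated AF; the documents give no interval between questionnaire and randomisation.

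**What to change.** Reconcile Study Population, Sample Size, Outcome assessments, the BAM section and Table 1 by stating one order for consent, questionnaires, index treatment, rhythm confirmation and randomisation. Which sequence applies is for the sponsor to decide. Then:

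- Use the randomisation date as time zero for time-to-treatment, person-months and QALYs.
- Require one baseline battery per patient, completed before allocation is revealed and at the same point relative to rhythm restoration for all patients.
- Record the date of the index procedure.
- State how EQ-5D is interpolated between baseline and month 6.
- If the baseline stays before the procedure, include the baseline score and the interval between baseline and procedure as covariates, and do not read within-group changes as intervention effects.

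The cost is protocol and SAP wording plus one date field. Further work arises only if the sponsor keeps a pre-procedure battery and also wants scores at randomisation: those patients would then need part or all of the ten instruments twice.
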